6.14.8 Assessment of Injection Sites

Descriptive statistics of injection site assessments will be reported. Mean, median, standard deviation, minimum, and maximum VAS scores will be presented for each time-point by dosing group (placebo, 0.005, 0.007, 0.011, 0.014, 0.021mg/kg).

Frequencies of severity (None, Mild, Moderate, Severe, Potentially Life Threatening) from injection site assessments performed by clinicians will be summarized by type (pain, tenderness, Erythema/Redness, Induration/Swelling) and timepoint, by dosage group.

Differences between placebo and active Scop HBT injection site VAS scores will be compared statistically by dosage level using three different ANOVA models corresponding to the first hour, next 4 hours, and 8 – 48 hours after injection. In the first model, VAS scores will be averaged over 10, 15, 30, & 45 minutes. In the second model, VAS scores will be averaged over 1, 1.5, 3, and 5-hour timepoints. The third model will include VAS scores averaged over 8, 12, 24, and 48-hour timepoints. VAS scores for active Scop HBT doses will be tested against scores for placebo using a one-sided alternative of higher scores for Scop HBT than placebo.

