unrelated to the study drug. The null hypothesis of no difference in DSST scores between active Scopolamine and placebo will be tested for each dose level using a one-sided alternative hypothesis of more negative changes in DSST scores among participants receiving the active drug than among the placebo group. A pooled analysis will compare all Scopolamine dosage levels to placebo. Individual participants' DSST scores will be presented by study day, and persistent declines in scores at Day 3 or Day 8 will be noted.

Frequencies of severity (None, Mild, Moderate, Severe, Potentially Life Threatening) from injection site assessments performed by clinicians will be summarized by type (pain, tenderness, erythema/redness, induration/swelling) and time point by dosage group. Semi-log graphs of mean VAS scores will be plotted (VAS score vs. log-time since injection). Differences between placebo and active drug injection site VAS scores will be compared statistically by dosage level using 3 different ANOVA models corresponding to the first hour, next 4 hours, and 8-48 hours after injection. A Wald test with a one-sided alternative will be used.

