5.1.10 Injection Site Assessments

At approximately 5 minutes after injection, the subject will be asked by the study staff to rate the maximum intensity of pain, pruritus, tingling, and numbness at the injection site using the VAS (*see protocol* Appendix A). The VAS will also be completed at pre dose and at 10, 15, 30, and 45 minutes and 1, 1.5, 3, 5, 8, 12, 24, and 48 hours post dose, and at Day 8. In addition, an injection site assessment for presence and severity of pain, tenderness, erythema, and induration/swelling will be performed by a physician, physician assistant, or nurse approximately 5 minutes after injection and for all subsequent time points (as stated above; *see protocol* Appendix C). Refer to *protocol* Appendix B for the Toxicity Grading Scale for Injection Site Reactions.

The anticipated neuropsychiatric effects of Scop HBT may hinder obtaining reasonable subjective data on the VAS, especially at the earlier post-dose time points. If the PI or designee determines a subject is incapable of providing valid responses at one or more time point(s), the reason(s) why the VAS assessment(s) could not be done will be documented by time point in the source documentation.

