6.3 HYPOTHESES AND DECISION RULES

As the objective of this study is to characterize the safety and tolerability of escalating doses of Scop HBT, three sets of safety endpoints will be compared statistically between placebo and active dosing groups. Some PK parameters will also be compared statistically across dose levels. Table 7 describes the hypothesis testing pre-specified in the statistical analysis.

The null hypothesis of no worse scores for Injection Site VAS (pain, itching, tingling, numbness); change in BPRS Score (6 hours, 48 hours, 8 days); change in DSST (48 hours, 8 days); and C-SSRS (SD 8) between dose levels of active Scop HBT and placebo will be tested statistically using a one-sided alternative of worse (higher for C-SSRS, VAS, and BPRS, lower for DSST scores for Scop HBT vs. placebo). Each dose level will be tested against the same placebo group (all participants receiving placebo). Methods for analysis of neuropsychiatric scales and injection site reactions are described in Sections 6.13.4 [6.14.6](#) and [6.14.8](#), respectively.

For PK parameters, variation across doses will be tested for T_{max} , $t_{1/2}$, V_d/F , Cl_F , and MRT against the null hypothesis of no difference across doses. A joint significance test (1 test per parameter) will be used.

Dose-proportionality will be tested using the dose-normalized parameters $C_{max}/Dose$ and $AUC_{\infty}/Dose$. A likelihood ratio test will be used for testing the joint null hypothesis of equivalence across all doses using a two-sided alternative. Each dose level will also be tested against the next dose level using a two-sided test. The methods for analysis and hypothesis testing are described in Section - [6.15](#). A total of 110 hypothesis tests will be performed. Procedures for multiple comparisons are detailed in Section [6.8](#).

Table 7: Pre-Specified Hypothesis Tests

Drug Characteristic	Null Hypothesis	Relevant Endpoints [Count]	Number of Comparisons Per Parameter	Total Number of Hypothesis Tests
Safety	Equivalence with Placebo	Injection site VAS (pain, itching, tingling, numbness) x (10-45 minutes, 1-5 hours, 8-48 hours) [12] Change in BPRS score from baseline (6 hours, 48 hours, SD 8) [3] Change in DSST scores from baseline (48 hours, SD 8) [2]	5 (Each dose level vs. Placebo)	90

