6.6.3 Handling of Other Missing Data

Other than AE data, for which missing will be imputed as the most severe, missing values will not be imputed for statistical summaries or analysis. All planned analyses of non-AE data will be conducted using all available data, including for participants who withdraw, with the exception of data to be censored following administration of rescue medications (as detailed in 6.11). In the event of study termination, all available data will be used for analysis of cohorts with at least one participant receiving the study drug.

Unless indicated otherwise, summary statistics will be reported for observed data only, with the exception of the cases described below.

Partial or incomplete start/end dates of the AEs or concomitant medications will be imputed to help determine treatment-emergent adverse events and prior or concomitant medications.

For incomplete start dates, following imputation rules will be implemented:

- Missing day - Impute as the 1st of the month unless month is same as month of first dose of study drug then impute using the day of first dose date.
- Missing day and month – impute as 1st January unless year is the same as first dose date then impute using the day and month of first dose date.

- Completely missing – impute using the first dose date unless the end date suggests it could have started prior to this in which case impute as 1st January of the same year as the end date.

When imputing a start date, ensure that the new imputed date is sensible i.e. is prior or equal to the end date of the AE or medication.

For incomplete end dates following imputation rules will be implemented:

- Missing day - Impute as the last day of the month unless month and year are the same as the month and year of the end of study, then impute as the end of study date.
- Missing day and month – Impute as 31st December unless year is the same as the year of the end of study date then impute as the end of study date.

Completely Missing – need to look at whether the AE/medication is still ongoing before imputing a date and also when it started in relation to study drug. If the ongoing flag is not missing then assume that AE is still present / medication is still being taken (i.e. do not impute a date). If the AE/medication has stopped and start date is prior to first dose date then impute as the 1st dose date, if it started on or after first dose date then impute as the end of study date.

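### VAS window averages will cover different time points in active and placebo subjects when early ratings are missed, so the one-sided injection-site tests are confounded with time

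*SAP*

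**What the plan says.** - **Analysis.** Protocol 12.1.2 compares VAS by dose level "using 3 different ANOVA models corresponding to the first hour, next 4 hours, and 8-48 hours after injection". SAP 6.14.8 keeps the three models and defines each response as an average over listed time points. For the first: "In the first model, VAS scores will be averaged over 10, 15, 30, & 45 minutes". The other two average 1 to 5 hours and 8 to 48 hours. The model has no time term. The test is one-sided, for higher scores on active drug.
- **Expected missingness.** SAP 5.1.10: "The anticipated neuropsychiatric effects of Scop HBT may hinder obtaining reasonable subjective data on the VAS, especially at the earlier post-dose time points". Protocol 11.1.7 says the same.
- **Handling.** For data other than adverse events, SAP 6.6.3 says "missing values will not be imputed for statistical summaries or analysis", and all available data are used. No section sets a minimum number of ratings per window or says how an incomplete window is averaged. No sensitivity analysis is planned.
- **Delayed ratings.** Footnote a to SAP Table 2 has a missed VAS done once the subject is able, without saying which time point it then represents.
- **5-minute rating.** It is collected (SAP 5.1.10: "At approximately 5 minutes after injection, the subject will be asked by the study staff to rate the maximum intensity of pain") and summarised descriptively. The first model is labelled as the first hour, but SAP Table 7 lists the windows as "10-45 minutes, 1-5 hours, 8-48 hours", so the omission is consistent within the SAP. No reason is given.

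**The concern.** A window average is a fair summary only if every subject contributes the same time points. Here the SAP itself attributes lost ratings to the drug, so completeness should differ between active and placebo and may differ between doses. If injection-site symptoms change over the window, a difference in averages mixes a treatment effect with a difference in when subjects were rated.

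At stake is the validity of a pre-specified safety comparison. If the mix lowers the active mean, the one-sided test loses sensitivity to local intolerance. If it raises the active mean, the test signals harm too often. Either way the p-values go into the 0.05 flag and the Benjamini-Hochberg procedure of SAP 6.8.

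**Working it through.** **Size of the affected family.** Four symptoms × 3 windows × 5 doses = 60 VAS tests, as in SAP Table 7. The first window has 4 × 1 × 5 = 20.

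**Plan's own figure.** Neither document gives a VAS effect size, standard deviation, missing rate or pain course. There is nothing to reproduce, so everything below rests on stated assumptions.

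**Expected shift with no true difference.** Assume VAS(t) = 3 × 2^(-(t-5)/h) cm in both arms and h = 20 minutes:

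- 10 min 2.52; 15 min 2.12; 30 min 1.26; 45 min 0.75
- all four: 6.66/4 = 1.66
- 30 and 45 only: 2.01/2 = 1.01
- 10 and 15 only: 4.64/2 = 2.32

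If half of active subjects miss 10 and 15 minutes, the shift is 0.5 × (1.01 - 1.66) = -0.33 cm, or 20% of 1.66. If they miss 30 and 45 instead, it is 0.5 × (2.32 - 1.66) = +0.33 cm. Varying h, with half of active subjects affected (cm):

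| h (min) | Full mean | Miss 10 | Miss 10, 15 | Miss 10, 15, 30 | Miss 30, 45 |
|---|---|---|---|---|---|
| 10 | 1.08 | -0.17 | -0.36 | -0.45 | +0.36 |
| 20 | 1.66 | -0.14 | -0.33 | -0.46 | +0.33 |
| 40 | 2.18 | -0.10 | -0.23 | -0.34 | +0.23 |

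Flat pain gives zero in every column.

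**Effect on the test.** Simulation of 20,000 trials per setting, with 6 active against 10 pooled placebo subjects (the smallest planned numbers) and a one-sided pooled t test at 0.05. Assumed: between-subject lognormal SD 0.4 and residual SD 0.3 cm. The declining course is 4 cm at time 0 with a 20-minute half-life; the rising course goes from 0.5 cm at time 0 to 2 cm at 45 minutes. The ratings missed are 10 and 15 minutes. Time-matched means that each rating is centred on the placebo mean at its own time before averaging. Entries are rejection rates:

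| Course, true active/placebo ratio | Complete | Half miss, plain average | All miss, plain average | Half miss, time-matched | All miss, time-matched |
|---|---|---|---|---|---|
| Declining, 1.0 | 5% | 0.6% | 0% | 4% | 2.5% |
| Declining, 1.5 | 58% | 20% | 2% | 49% | 39% |
| Declining, 2.0 | 93% | 61% | 22% | 88% | 82% |
| Rising, 1.0 | 5.5% | 16% | 34% | 6% | 7% |

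With declining pain, no true difference and all active subjects missing both ratings, the mean difference is -0.74 cm with plain averaging and 0.00 cm with time matching. With a true ratio of 1.5 and all missing, the plain difference turns negative (-0.18 cm). At a ratio of 2 it stays positive (+0.39 cm).

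**Other readings of the unstated rule.** Dropping subjects with an incomplete window keeps only the least impaired of 6 to 9 active subjects. Entering a delayed rating in the missed slot puts a later score under an earlier label. Neither restores the comparison.

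**5-minute rating.** With complete data and the same 20-minute course in both arms, including 5 minutes changes the window mean from 1.87 to 2.17 cm in both, so no difference between arms arises. For a subject who misses 10 and 15 minutes, adding it changes the shift in that subject's mean from -40% to -13% if 5 minutes was rated, but to -48% if it was missed too.

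**The case against.** The strongest reply is that the SAP never says it averages whatever ratings are present. That is inferred from the all-available-data rule and the lack of imputation. This stands: the fault is an average with no rule for gaps, not a declared biased rule. But no reading of the silence repairs the comparison.

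A reader might infer that impaired subjects will look less painful than placebo. The documents do not support that. They give no pain course and do not say which early ratings will be lost. Protocol 5.2.4 cites an intravenous study in which alertness and psychedelic effects lagged plasma with equilibration half-lives of 2.5 to 3.5 hours, so loss of the later ratings in the first hour is also plausible. That reverses the sign. Even with declining pain, a true excess may only shrink.

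A reader might also blame the missing 5-minute rating. It is left out for both arms and causes no difference between them. Nothing shows that it would be the most complete early rating.

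Safeguards exist. VAS is summarised at every time point by dose, and clinicians grade the site at the same times. Missing data are tabulated with causes (SAP 6.6.1), nonzero VAS scores are recorded as adverse events (Protocol 11.1.7), and severe reactions count as nonextreme DLTs. SAP 6.1 makes the objectives primarily descriptive. So local intolerance would not go unseen. These safeguards expose the problem but do not correct the tests.

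**Conclusion.** The concern holds in conditional form. The planned averages can compare active and placebo over different time points, for a reason that the SAP itself foresees, and nothing in the plan corrects the tests.

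The direction is not known. Under the assumed declining course with half of active subjects affected, the shift is -0.10 to -0.46 cm when the earliest ratings are lost and +0.23 to +0.36 cm when 30 and 45 minutes are lost. It is zero if pain is flat. These sizes rest on the assumed start, half-lives and missing fraction; the power figures also rest on the assumed SDs.

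The concern falls mainly on the 20 first-window tests. A reader might count all 60 VAS tests, but the SAP expects the loss especially at early ratings. The 5-minute omission is a separate, smaller point of unexplained scope.

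**What to change.** - In SAP 6.14.8, replace the subject-average ANOVA in each window with a repeated-measures model of the individual ratings: dose group, time point as a factor, and a subject effect. An equivalent time-matched contrast would also do. Keep the one-sided dose-versus-placebo test, so the count of 60 is unchanged.
- State which time point a delayed rating under Table 2 footnote a counts for.
- Include the 5-minute rating in the first window or give the reason for leaving it out.

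**Cost.** SAP wording and modest programming before unblinding; no new data. A covariance structure must be specified with 6 to 9 active subjects per dose, and the bootstrap fallback in SAP 6.10 must resample whole subjects.

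**Limits.** Matching on time removes the time mix, but bias remains if missingness depends on unobserved pain. Some loss also remains if the dose effect itself fades over the window: at a true ratio of 1.5 with all active subjects missing 10 and 15 minutes, the time-matched difference was 0.56 cm against 0.93 cm with complete data. The simple centring used in the check was also not exactly calibrated (2.5% to 7% in the settings shown), which is a reason to prefer the fitted model.

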6.14.9 Medical History

Medical History data will not be tabulated but will be provided in a listing by cohort, dose level, and subject.

6.14.10 Concomitant Medications

Concomitant Medications will be coded using the World Health Organization (WHO) Drug dictionary, using Anatomical Therapeutic Chemical (ATC) classifications and WHO preferred terms. Concomitant Medications will not be tabulated but will be provided in a listing by cohort, dose level, and subject.

6.15 PHARMACOKINETIC ANALYSES

6.15.1 Plasma Pharmacokinetics

The estimation of pharmacokinetic parameters of interest is not described within this SAP. A separate PK report will detail methods and limitations of the estimation of PK parameters. However, PK parameters will be analyzed as part of this SAP.

PK parameters will be assessed for homoskedasticity prior to modeling using ANOVA. For parameters that vary by orders of magnitude across dose groups, a logarithmic transformation will be carried out prior to testing for homogeneity of variance. Otherwise a likelihood ratio test for homogeneity of variance will be carried out on the untransformed PK values or on transformed values, as appropriate. The tests for homogeneity of variance will exclude outlying values. If there are significant differences ($p < 0.05$) in variances across dose groups, comparison of PK means across dose groups will be carried out based on a heterogeneous variance analysis of variance. Otherwise it will be carried out based on a homogeneous variance analysis of variance.

Dose-equivalency of five PK parameters (T_{max} , $t_{1/2}$, V_d/F , CL_F , MRT) will be tested using ANOVA. Models will adjust for sex of the subject. Equation 3 presents the model to be used for all ANOVA of PK parameters,

$$G(Y_i) = \beta_0 + \beta_1 \times I(D_i = 2) + \beta_2 \times I(D_i = 3) + \beta_3 \times I(D_i = 4) + \beta_4 \times I(D_i = 5) + \beta_5 \times Sex_i + \varepsilon_i \quad (8)$$

, where G is a link function (or identity), Y_i is the PK parameter of interest i , β_0 is the change in PK parameter for the placebo group, D_i is the dosage level ($1=0.005$, $2=0.007$, $3=0.011$, $4=0.014$, $5=0.021$ mg/kg), and ε_i is an error term each for participant i . Models will control for the sex of the participant. The significance of the difference in parameters by dose level will be tested using a likelihood ratio test for the joint null hypothesis: $H_0: \beta_1 = \beta_2 = \beta_3 = \beta_4 = 0$. If bootstrapping is used, a null distribution will be generated using an F-statistic, as described previously. For parameters where dose-proportionality is assessed, the equivalency of each parameter with the next higher dose level will be tested, using the null hypotheses:

$$\begin{aligned} \beta_0 &= \beta_0 + \beta_1 \text{ i.e. } \beta_1 = 0 \\ \beta_0 + \beta_1 &= \beta_0 + \beta_2 \text{ i.e. } \beta_1 = \beta_2 \\ \beta_2 &= \beta_3 \\ \beta_3 &= \beta_4 \\ \beta_4 &= \beta_5 \end{aligned} \quad (9)$$

Two PK parameters, C_{\max} and AUC_{∞} , will also be used to test dose-proportionality. ANOVA models will compare C_{\max}/Dose and AUC_{∞}/Dose across active dose levels. Joint significance will be tested using likelihood ratio tests. Individual doses will be compared to the next higher dose using Wald Tests of model parameters.

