5.2.1 Plasma Pharmacokinetics

The PK parameters will not be calculated as part of this SAP, but they will undergo statistical analysis according to this SAP. The PK parameters will be calculated by the Battelle Chemistry Technical Center according to their Standard Operating Procedures and conventions, using WinNonlin Phoenix v8.1). Plasma concentration time profiles for each subject tested will be evaluated using semi-log plots and characterized using noncompartmental analysis.

Descriptive statistics for the concentration of Scopolamine in plasma and for the PK parameters will be calculated at each scheduled time point. The summary of descriptive statistics at each time point will be displayed by cohort and dose level. The statistics will include sample size, mean, median, standard deviation (SD), standard error of the mean (SEM), percent coefficient of variance (CV), minimum, and maximum for continuous variables, and 95% confidence intervals. Additionally, geometric means will be calculated for AUC_{∞} and C_{max} .

Analysis of plasma concentrations will be performed for each subject on samples collected prior to dosing and at the following post-dose target time points: 2, 5, 10, 15, 20, and 30 minutes and 1, 2, 4, 8, 12, 24, 36, and 48 hours post dose. Table 6 describes the time windows for blood draw. PK parameters will be calculated using the time points of the actual blood draw, rather than the target time. The serum PK parameters that will be analyzed are listed below and are outlined and defined as in the protocol:

- **C_{max}** : Maximum measured plasma concentration over the time span specified.
- **T_{max}** : Time of maximum measured plasma concentration. If the maximum value occurs at more than one time point, T_{max} is defined as the first time point with this value.
- **$t_{1/2}$** : Apparent first-order terminal elimination half-life will be calculated as $0.693/k_e$.
- **V_d/F** : Apparent Volume of distribution.
- **Cl/F** : Apparent Volume of blood or plasma cleared of drug per unit time.
- **MRT (Mean Residence Time)**: Mean time the drug spends in the body before being eliminated.
- **AUC_{last}** : The area under the plasma concentration versus time curve, from time 0 to the last measurable concentration, as calculated by the linear trapezoidal method.

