6.10 DISTRIBUTIONAL ASSUMPTIONS

The residuals of ANOVA models will be assessed for normality using a Shapiro-Wilk test in conjunction with visual inspection of quantile-quantile plots. Lognormality is commonly assumed for PK parameters. If the normality assumption is not met, logarithmic (natural or base-10) transformation will be assessed. If lognormality is rejected, non-parametric bootstrap replication with a minimum of 10,000 replications will be used to calculate confidence intervals and perform hypothesis testing.

With small samples, the normality of parameters, such as the sample mean, cannot be assured. Therefore, quantile-based confidence intervals will be obtained, and hypothesis testing will be conducted using comparisons of observed test statistics to test statistics obtained under the null hypothesis. For hypotheses of equivalence between two populations (e.g. placebo and dosage groups, $\beta_1 = 0, \mu_1 = \mu_2$), an unequal sample unequal variance T-statistic will be used:

$$T = \frac{\widehat{\mu}_1 - \widehat{\mu}_2}{s_p \sqrt{\frac{1}{n_1} + \frac{1}{n_2}}} \quad (1)$$

where, $\widehat{\mu}_1$ and $\widehat{\mu}_2$ are the observed sample means, and

$$s_p = \sqrt{\frac{(n_1-1)s_1^2 + (n_2-1)s_2^2}{n_1+n_2-2}} \quad (2)$$

Where s_1^2 and s_2^2 are the sample variances. The null distribution will be generated by resampling from the values at their two groups shifted to their pooled sample mean.

For joint significance tests (e.g. $H_0: \beta_1 = \beta_2 = \beta_3 = \beta_4 = 0$), the F-statistic will be used with the formula,

$$F_b = \frac{\left(\frac{RSS_1 - RSS_2}{p_2 - p_1}\right)}{\left(\frac{RSS_2}{n - p_2}\right)} \quad (3)$$

where RSS_1 is the residual sum of squares for an ANOVA model fit under the null with p_1 parameters and RSS_2 a model fit with all parameters p_2 included. The null distribution will be generated through resampling from the distributions of each dosage cohort shifted to their common mean. With bootstrap resampling, p-values will be calculated by comparing observed values of the test statistic to the null distribution:

$$p = \frac{1}{B} \sum_{b=1}^B I(F_b \geq F_{obs} \text{ or } |T_b| \geq |T_{obs}|) \quad (4)$$

where B is the number of bootstrap samples taken.

ANOVA also assumes homogeneity of variance (i.e. homoskedasticity). Homogeneity of variance will be assessed. If variances are equal, homogenous variance ANOVA will be

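### The SAP picks the analysis scale of each PK parameter by a normality pretest, so the joint tests of CL/F and AUCinf/Dose, which are reciprocals in one dose unit, need not agree

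*SAP*

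**What the plan says.** Three parts of the SAP bear on the scale of the PK tests.

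- **Magnitude rule (SAP 6.15.1).** "For parameters that vary by orders of magnitude across dose groups, a logarithmic transformation will be carried out" before homogeneity of variance is tested. For all other parameters the text leaves the scale open: "Otherwise a likelihood ratio test for homogeneity of variance will be carried out on the untransformed PK values or on transformed values, as appropriate".
- **Normality check (SAP 6.10).** "The residuals of ANOVA models will be assessed for normality using a Shapiro-Wilk test in conjunction with visual inspection of quantile-quantile plots". The section remarks that "Lognormality is commonly assumed for PK parameters", yet the log comes second: "If the normality assumption is not met, logarithmic (natural or base-10) transformation will be assessed". If lognormality is rejected too, a bootstrap is used. Protocol 12.5 has a similar order, with link functions assessed only if normality fails.
- **Descriptive summary (SAP 5.2.1).** "Additionally, geometric means will be calculated for" AUCinf and Cmax, so the summary is already partly on a ratio scale.

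On what is tested, SAP 6.3 states that "variation across doses will be tested for" Tmax, t1/2, Vd/F, CL/F and MRT, one joint test each. SAP 6.15.1 repeats this as "Dose-equivalency of five PK parameters". Cmax/Dose and AUCinf/Dose each get a joint test and four adjacent-dose tests. Table 7 counts the CL/F and AUCinf/Dose joint tests in separate rows of a family of 110. The dose-equivalence list in Protocol 12.1.1 has Tmax, t1/2, Vd and MRT; the SAP adds CL/F.

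**The concern.** Whether a PK parameter is compared by arithmetic difference or by ratio depends on a check run on that parameter's own residuals, about 30 of them if every cohort has 6 active subjects. For most parameters this is only untidy. CL/F and AUCinf/Dose are different, because they carry the same information. If one stays untransformed and the other is logged, or if both stay untransformed, their joint tests need not agree. The report could then mark AUCinf/Dose as differing across doses and CL/F as not differing, or the reverse, and the SAP has no rule for which result governs. Dose proportionality of AUCinf is a stated objective (SAP 2, Protocol 12.1).

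**Working it through.** **1. The SAP's own figures.** SAP 6.14.6 has C-SSRS tested at each dose as well as pooled. On that count Table 7 gives (12 + 3 + 2 + 1) x 5 = 90 tests by dose, 5 pooled safety tests, 5 PK dose-equivalence tests and 2 x (1 + 4) = 10 proportionality tests: 90 + 5 + 5 + 10 = 110. The Benjamini-Hochberg thresholds k x 0.20/110 for k = 1 to 5 are 0.0018, 0.0036, 0.0055, 0.0073 and 0.0091, as SAP 6.8 prints.

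**2. Can the magnitude rule apply?** The dose range is 0.021/0.005 = 4.2-fold. If a dose-normalised parameter changes as dose^b, its mean changes 4.2^b-fold over the range: 4.2^0.3 = 1.5 and 4.2^0.5 = 2.0. Even one order of magnitude needs b = ln 10/ln 4.2 = 2.303/1.435 = 1.6. The rule is therefore very unlikely to be triggered, and the SAP 6.10 check decides.

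**3. Are the two tests one hypothesis?** The documents define CL/F in words only. Protocol Table 9 gives Vz/F = Dose/AUCinf/λz, so CL/F = λz x Vz/F = Dose/AUCinf = 1/(AUCinf/Dose), provided that Dose is in the same unit in both. Then log(CL/F) = -log(AUCinf/Dose). On the log scale every model coefficient changes sign, the residual sums of squares are unchanged, and the joint p-values are identical. On the raw scale the mean of 1/x is not 1/(mean of x), so nothing makes the p-values match. Only the joint test is duplicated; the adjacent-dose tests apply to AUCinf/Dose alone.

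**4. Variability (assumption).** The documents state no between-subject CV. Protocol 5.2.2 gives AUC 0.94 ± 0.52 based on a 99% CI. Assuming n = 6, the CV is 0.52 x √6/(4.03 x 0.94) = 34% with a t quantile, or 0.52 x √6/(2.576 x 0.94) = 53% with a normal quantile. If 0.52 is an SD, it is 55%. The range examined is 30-66%.

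**5. Simulation.** Five doses, lognormal AUCinf/Dose with CL/F as its reciprocal, log-log slope 0.3-0.5, joint test at two-sided 0.05, and Shapiro-Wilk at 0.05 choosing raw or log for each parameter.

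| Quantity | Result |
|---|---|
| Different scales, 6 per dose | about 40-60% of trials |
| Different sides of 0.05, 6 per dose | about 2-10% |
| Different sides of 0.05, 9 per dose | 0-6% |
| Both prespecified on log scale, one dose unit | 0% (algebra) |
| Power for AUCinf/Dose, CV 50%, slope 0.5, 6 per dose | pretest rule 54%, log 55% |

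In discordant pairs at 6 per dose, the median p-values were about 0.03-0.04 and 0.06-0.08, and the larger p was below 0.15 in 92-100% of them.

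**6. Sensitivity.** Adding the sex covariate, likelihood ratio tests and the unequal-variance branch, with 6 per dose and CV 30-60%, discordance was 4-7% under exact proportionality and 11-14% with a 1.5-fold shift at the top dose only. It was 2-9% for a 2-fold trend (CV 30% and 45%). With 9 per dose, the top-dose shift and the normality pretest only, it was about 5-8%. Q-Q judgement, the bootstrap fallback and the outlier screen were not simulated.

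**7. One illustration.** This simulated data set was picked because it shows the effect (6 per dose, CV 30%). Both parameters pass Shapiro-Wilk (p of 0.50 or more) and variances are homogeneous, so both stay untransformed. The joint likelihood ratio p is 0.007 for AUCinf/Dose and 0.057 for CL/F. On the log scale both are 0.020.

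**8. Dose unit.** The documents do not say whether Dose is mg or mg/kg. If the two parameters differ in this, they differ by body weight (55-85 kg allowed). Log-scale tests then disagreed in 2-17% of simulated trials, with weights assumed uniform.

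**The case against.** The strongest reply is that the SAP is less rigid than a Shapiro-Wilk rule. It adds Q-Q plots, allows transformed values where judged suitable, writes the model with a link function and has a bootstrap fallback. SAP 6.1 addresses the objectives mainly by descriptive statistics, and SAP 6.8 calls the trial exploratory with a false discovery rate of 0.20. SAP 6.7.2 keeps statistical tests out of the board's decisions to halt or terminate. All of this stands and limits the weight of the point. The flexibility does not cure the inconsistency, because it can be used differently for each of the two reciprocals.

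A reader might infer more than the documents support:

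- *That the tests will contradict each other.* Discordance here means one p-value on each side of 0.05, usually close to it.
- *That the rate is 5-23%, or that power falls from 55% to 46%.* Those figures belong to an analysis fixed on the raw scale, which the SAP does not prescribe. The pretest rule recovers nearly all the power.
- *That the log scale alone guarantees agreement.* It does so only with one dose unit.
- *That adding CL/F is an error.* SAP 1 lets the SAP supersede the protocol, and SAP 6.2 allows additional analyses specified before unblinding.
- *That ANOVA for Tmax is a defect.* Tmax is close to discrete, but actual draw times are used and the bootstrap is available; a rank test is a preference.

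**Conclusion.** The point holds as a refinement worth considering, not as a required correction. The SAP lets the scale vary by parameter, and it tests one joint hypothesis twice if a common dose unit is used. At 6 active per dose the duplicate tests fall on different sides of 0.05 in about 2-10% of trials under a log-log trend, somewhat more for a shift confined to the top dose. At 9 per dose the figure under a log-log trend is 0-6%. These rates rest on assumed lognormality, CVs and departures. The effect on power and on the multiplicity thresholds is negligible, and no escalation decision uses these tests. What is gained is one consistent answer on AUCinf proportionality.

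**What to change.** - In SAP 6.10 and 6.15.1, prespecify natural-log analysis for Cmax/Dose, AUCinf/Dose, Vd/F, t1/2 and MRT, and report geometric mean ratios between adjacent doses with confidence intervals. Keep the residual checks as diagnostics.
- State one dose unit, mg or mg/kg, for all dose-normalised and apparent parameters, and give the CL/F formula.
- Keep CL/F descriptive, drop its joint test, and set the Table 7 total to 109. The five lowest thresholds become k x 0.20/109: 0.0018, 0.0037, 0.0055, 0.0073 and 0.0092.
- Optionally, use a rank test for Tmax.

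The cost is SAP wording, made before unblinding, and one test fewer. No further data are needed.
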